5.1.4 Monitoring of dose administration

Subjects will be monitored before, during and after the infusion with assessment of vital signs at the times specified in the Schedule of Assessment. Subjects are monitored (pulse rate, blood

Clinical Study Protocol

Drug Substance Durvalumab (Medi4736)

Study Number MCC 18788/MCC18788/ESR-15-11326

Edition Number 1.9.4

Date **10/08/2018**

pressure) every 30 minutes during the infusion period (including times where infusion rate is slowed or temporarily stopped).

In the event of a \geq Grade 2 infusion-related reaction, the infusion rate of study drug may be decreased by 50% or interrupted until resolution of the event (up to 4 hours) and re-initiated at 50% of the initial rate until completion of the infusion. For subjects with a \leq Grade 2 infusion-related reaction, subsequent infusions may be administered at 50% of the initial rate. Acetaminophen and/or an antihistamine (e.g., diphenhydramine) or equivalent medications per institutional standard may be administered at the discretion of the investigator. If the infusion-related reaction is Grade 3 or higher in severity, study drug will be discontinued. The standard infusion time is one hour, however if there are interruptions during infusion, the total allowed time from infusion start to completion of infusion should not exceed 4 hours at room temperature, with maximum total time at room temperature not exceeding 4 hours (otherwise requires new infusion preparation).

As with any antibody, allergic reactions to dose administration are possible. Appropriate drugs and medical equipment to treat acute anaphylactic reactions must be immediately available, and study personnel must be trained to recognize and treat anaphylaxis. The study site must have immediate access to emergency resuscitation teams and equipment in addition to the ability to admit subjects to an intensive care unit if necessary.

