Severity Grade of the Event (NCI CTCAE version 4.03)	Dose Modifications	Toxicity Management
Any Grade	General Guidance	For Any Grade: 
– Manage per institutional standard at the discretion of investigator.– Monitor patients for signs and symptoms of infusion-related reactions (e.g., fever and/or shaking chills, flushing and/or itching, alterations in heart rate and blood pressure, dyspnea or chest discomfort, or skin rashes) and anaphylaxis (e.g., generalized urticaria, angioedema, wheezing, hypotension, or tachycardia).
Grade 1 or 2	For Grade 1: 
The infusion rate of study drug/study regimen may be decreased by 50% or temporarily interrupted until resolution of the event.
 For Grade 2: 
The infusion rate of study drug/study regimen may be decreased 50% or temporarily interrupted until resolution of the event.
 
Subsequent infusions may be given at 50% of the initial infusion rate.
	For Grade 1 or 2: 
– Acetaminophen and/or antihistamines may be administered per institutional standard at the discretion of the investigator.– Consider premedication per institutional standard prior to subsequent doses.– Steroids should not be used for routine premedication of Grade ≤ 2 infusion reactions.
Grade 3 or 4	For Grade 3 or 4: 
Permanently discontinue study drug/study regimen.
	For Grade 3 or 4: 
– Manage severe infusion-related reactions per institutional standards (e.g., IM epinephrine, followed by IV diphenhydramine and ranitidine, and IV glucocorticoid).

CTCAE Common Terminology Criteria for Adverse Events; IM intramuscular; IV intravenous; NCI National Cancer Institute.

Clinical Study Protocol

Drug Substance Durvalumab (Medi4736)

Study Number MCC 18788/MCC18788/ESR-15-11326

Edition Number 1.9.4

Date **10/08/2018**

Non-Immune-Mediated Reactions

Severity Grade of the Event (NCI CTCAE version 4.03)	Dose Modifications	Toxicity Management
Any Grade	Note: Dose modifications are not required for AEs not deemed to be related to study treatment (i.e., events due to underlying disease) or for laboratory abnormalities not deemed to be clinically significant.	Treat accordingly, as per institutional standard.
Grade 1	No dose modifications.	Treat accordingly, as per institutional standard.
Grade 2	Hold study drug/study regimen until resolution to \leq Grade 1 or baseline.	Treat accordingly, as per institutional standard.

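### Section 5.1.4 lets an infusion be slowed or restarted for any reaction of Grade 2 or higher, with no upper limit, although the same paragraph discontinues drug at Grade 3 or higher

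*Combined protocol and SAP*

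**What the plan says.** Section 5.1.4 of the protocol (Monitoring of dose administration) gives three grade-based instructions in one paragraph.

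- Current infusion: "In the event of a \geq Grade 2 infusion-related reaction, the infusion rate of study drug may be decreased by 50% or interrupted until resolution". After an interruption of up to 4 hours, the infusion is restarted: "and re-initiated at 50% of the initial rate until completion of the infusion".
- Later infusions: "For subjects with a \leq Grade 2 infusion-related reaction, subsequent infusions may be administered at 50% of the initial rate".
- Stopping, three sentences after the first instruction: "If the infusion-related reaction is Grade 3 or higher in severity, study drug will be discontinued".

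The Infusion-Related Reactions table in Appendix A handles the same events by grade. At Grade 1: "The infusion rate of study drug/study regimen may be decreased by 50% or temporarily interrupted until resolution of the event". Grade 2 carries nearly the same sentence, followed by "Subsequent infusions may be given at 50% of the initial infusion rate". At Grade 3 or 4: "Permanently discontinue study drug/study regimen".

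Section 4.3 item 6 lists an infusion reaction of Grade 3 or above as a reason for permanent discontinuation. Section 6.3 does the same for Grade 3 toxicity at least possibly related to durvalumab.

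**The concern.** A threshold of Grade 2 or higher takes in Grades 3 and 4. Read literally, the first sentence therefore allows staff to slow the infusion, or pause and restart it, and run it to completion after a severe or life-threatening reaction. The fourth sentence of the paragraph requires drug to be discontinued for that same reaction.

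The decision is made at the bedside while the reaction is under way, and the restart permission comes before the stopping rule. Section 10.1.5 itself recognises that acute allergic reactions can be severe or fatal. With two to three centers planned, sites could also handle the same grade of reaction differently. What is at stake is subject safety and uniform conduct, not the efficacy inference.

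**Working it through.** No figure in the plan depends on this point, so the check is a grade-by-grade comparison. Inputs: Section 5.1.4, the Appendix A infusion-reaction table, Section 4.3 item 6 and Section 6.3.

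| Action | Section 5.1.4 | Appendix A | Section 4.3 item 6 |
|---|---|---|---|
| Slow or interrupt the current infusion (5.1.4 adds restart at half rate) | Grades 2, 3, 4 | Grades 1, 2 | not addressed |
| Later infusions at half rate | Grades 1, 2 | Grade 2 (as the table appears to print it) | not addressed |
| Discontinue drug | Grade 3 or higher | Grades 3, 4 | Grade 3 or higher |

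**Step 1, inside 5.1.4.** The first and third rows overlap: {2, 3, 4} and {3 or higher} share Grades 3 and 4. For those grades one sentence permits completing the infusion and another ends treatment. The first sentence contains no exception that would separate them.

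**Step 2, discontinuation.** The third row agrees everywhere. Section 6.3 points the same way. There is no disagreement about the grade at which drug is stopped.

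**Step 3, current infusion against Appendix A.** {2, 3, 4} and {1, 2} differ at Grades 1, 3 and 4. At Grades 3 and 4 this is the Step 1 conflict seen from outside the section. At Grade 1, Appendix A gives an optional action and 5.1.4 says nothing.

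**Step 4, later infusions.** {1, 2} and {2} differ at Grade 1 only. Section 5.1.4 gives an optional action and Appendix A appears to say nothing.

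**Step 5, which text governs.** Section 6.2 sends the reader to 5.1.3 and 5.1.4 for administration and monitoring. Section 6.3 sends the reader to the Appendix A tables for infusion-related reactions. Section 10.1.5 points to a Section 6.6.1, but Section 6 ends at 6.3. No cross-reference says which text prevails.

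**Step 6, dependence on the printed sign.** The text available was machine-read. If the first sign in the source is in fact Grade 2 or lower, the current-infusion set becomes {1, 2}. The overlap with discontinuation then disappears and the row agrees with Appendix A; only the Grade 1 difference for later infusions remains. The two signs were read as different symbols in adjacent sentences, which argues against a uniform reading error but does not replace a look at the PDF.

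**The case against.** The strongest reply is that no careful reader would restart after a Grade 3 reaction. The stopping sentence is mandatory and the restart sentence only permissive; the stopping rule sits in the same paragraph; and Sections 4.3 and 6.3 and Appendix A all agree with it. Section 6.3 also names the Appendix A tables as the place for managing these reactions. This lowers the risk and should be granted. It does not remove the contradiction: the paragraph still states a permission that it withdraws three sentences later, without saying that it does so.

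A second reply concerns Grade 1. A reader might infer that Grades 1, 3 and 4 all receive contradictory instructions. The documents do not support that for Grade 1. Each text offers an option where the other is silent, both can be followed together, and Appendix A leaves management at any grade to institutional standard and investigator discretion. Moreover, placing the later-infusion sentence under Grade 2 alone rests on its position in a flattened table row headed for Grades 1 and 2 together. This reply stands.

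A reader might also infer that Section 5.1.4 departs from Appendix A on every threshold. It does not, because the discontinuation threshold matches. Nor do the documents show that the amount of drug given at Grade 1 would vary between sites: Section 5.1.3 requires the whole bag to be infused.

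**Conclusion.** The point holds in a limited form. As printed, Section 5.1.4 contradicts itself for Grade 3 and 4 reactions, and its restart sentence conflicts with Section 4.3 item 6, Section 6.3 and Appendix A. The cause is one sentence without an upper grade limit. The Grade 1 mismatch is secondary and is a difference in coverage.

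The size cannot be put as a number of events. A reader might take 13 doses × 34 subjects = 442 infusions as the scale, but that counts planned infusions, not reactions. It is not a firm ceiling either: replaced subjects add infusions, and a stop after stage 1 would leave about 13 × 13 = 169.

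The conclusion assumes that the first inequality sign was read correctly from the PDF. The Grade 1 remark on later infusions also assumes that the table line was assigned to the right grade. The endpoint, sample size, type I error and power are unaffected. The correction is still worth making promptly, because it concerns a stop-or-restart instruction for severe reactions.

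**What to change.** First check both inequality signs in Section 5.1.4, and the layout of the Appendix A table, against the source PDF. Then reconcile Section 5.1.4 with Section 4.3 item 6, Section 6.3 and the Appendix A infusion-reaction table, so that each grade appears once, with one stated action for the current infusion and one for later infusions. State which text governs, and repair the Section 10.1.5 reference at the same time.

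The choice of rule belongs to the sponsor and investigators. Simply flipping the signs is not a safe shortcut: reversing the second one would apply the later-infusion provision to Grades 2, 3 and 4 and create a new overlap with discontinuation.

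The cost is an amendment of about one paragraph and a note to infusion and pharmacy staff at each site. No statistical section needs to change.

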5.1.5 Accountability and dispensation

Research pharmacy at each investigational site will be responsible for Durvalumab accountability and dispensation. The investigator's or site's designated investigational product manager is required to maintain accurate investigational product accountability records. Upon completion of the study, copies of investigational product accountability records will be returned to MedImmune.

5.1.6 Disposition of unused investigational study drug

All unused investigational product will be returned to a MedImmune authorized depot or disposed of upon authorization by MedImmune. The sites will account for all investigational study drug dispensed and also for appropriate destruction. Certificates of delivery and destruction must be signed.

6. TREATMENT PLAN

6.1 Subject enrollment

Subjects with BCG refractory CIS urothelial carcinoma of the bladder as defined in inclusion criteria will be consented and screened.

Subjects who have completed 6 or more doses of Durvalumab and underwent month 6/week 26 bladder biopsy would be considered evaluable. Subjects who completed less than 6 doses of durvalumab will not be considered evaluable but will be followed until after the month 24 cystoscopic evaluation and biopsy. Subjects who withdrawn from the study prior to the month 6 cystoscopic evaluation and biopsy would be replaced to ensure a total of 34 evaluable subjects.

Subjects who are incorrectly enrolled but are not yet initiated on treatment should be withdrawn from the study.

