Sample Size Determination: The null hypothesis is the 18% historical complete response rate at month 6 will be tested against a one-sided alternative of 40% or higher complete response rate with Durvalumab at month 6 in BCG refractory CIS of bladder. We use a Simon's two-stage design (Simon, 1989) based on the optimal two-stage designs and admissible designs (Jung et al. 2004) for Phase II single arm clinical trials. The required total number of subjects is 34. 13 is the number of subjects accrued during stage 1. If 3 or fewer responses are observed during stage 1, the trial is stopped early for futility. If 9 or fewer responses of total 34 patients are observed by the end of stage two, then no further investigation of the drug is warranted. This design yields a one-sided type I error rate of 0.047 and power of 80% when the true response rate is 40% based on Simon's optimal two-stage design.

SCHEDULE OF STUDY ASSESSMENTS**Schedule of study assessments: Screening and Treatment Period (<<12 months: maximum of 13 doses, last infusion week 50>>)**

Assessments to be performed at the times stipulated in the table and as clinically required in the management of the subject.	Screening	All assessments to be performed pre-infusion unless stated otherwise				
		Baseline	Every 4 weeks	Every 3 months of 12 months treatment phase	Every 4 months of the 12 months surveillance phase	End of Trial visit
Day	-28 to -1	1	Day 1 of the week			
Week	-4 to -1	0	4, 8, 12, 16, 20, 24, 28, 32, 36, 40, 44, 48, (± 3 days)	14, 26, 38, 52 (± 14 days)	68, 86 104, (±14 days)	105 (±7 days)
Written informed consent/assignment of subject identification number	X					
Demography and history of tobacco and alcohol use	X					
Previous treatments for CIS of bladder	X					
Formal verification of eligibility criteria	X					
Hepatitis B and C; HIV	X					
Urine hCG or serum βhCG ^b	X	As clinically indicated				
Durvalumab administration		X	X			
Clinic visit with history and physical examination ^c	X	X	X		X	X

Schedule of study assessments: Screening and Treatment Period (<<12 months: maximum of 13 doses, last infusion week 50>>)

Assessments to be performed at the times stipulated in the table and as clinically required in the management of the subject.	Screening	All assessments to be performed pre-infusion unless stated otherwise					
		Baseline	Every 4 weeks	Every 3 months of 12 months treatment phase	Every 4 months of the 12 months surveillance phase	End of Trial visit	

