5.1.2 Durvalumab Doses and treatment regimens

Treatment with fixed dose durvalumab at 1500 mg Q4W durvalumab (equivalent to 20 mg/kg Q4W, based on an average body WT of 75 kg) commences on Day 1 following confirmation of eligibility into the study and continues on a Q4W schedule for a maximum duration of treatment of 12 months (maximum of 13 doses). Study treatment should be discontinued prior to 12 months if there is confirmed PD (unless the investigator considers the subject to continue to receive benefit from treatment), initiation of alternative cancer therapy,

unacceptable toxicity, withdrawal of consent, or if other reasons to discontinue study treatment occur.

Subjects who have a dose interruption due to toxicity at any point in the first 12 months of treatment may resume treatment and complete the 12-month treatment period.

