9. DISEASE EVALUATION AND METHODS

The response to immunotherapy may differ from the typical responses observed with cytotoxic chemotherapy including the following (Wolchok et al 2009, Nishino et al 2013):

- Response to immunotherapy may be delayed
- Response to immunotherapy may occur after PD by conventional criteria
- The appearance of new lesions may not represent PD with immunotherapy
- SD while on immunotherapy may be durable and represent clinical benefit.

Based on the above-described unique response to immunotherapy, subjects with persistent CIS at the month 3 bladder biopsy will continue to receive Durvalumab until the month 6 bladder biopsy documented persistent CIS or progression to the muscle invasive stage. Durvalumab will be discontinued and subjects will be off study if invasive bladder cancer (T1 or above) is documented in any of the bladder biopsies. Due to the nature of CIS of bladder, RECIST 1.1 or irRECIST will not be applicable to response assessment.

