11.1.2 Efficacy analysis set

Subjects who have completed at least 6 treatments of every 4 week Durvalumab IV infusions and underwent the month 6 mapping biopsy will be included in the efficacy analysis set. Intention to treat analysis will be performed on all subjects who have completed at least one dose of Durvalumab and underwent the month 6 mapping biopsy.

Clinical Study Protocol

Drug Substance Durvalumab (Medi4736)

Study Number MCC 18788/MCC18788/ESR-15-11326

Edition Number 1.9.4

Date 10/08/2018

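### The six-dose evaluability rule sets no date by which the doses must have been given, so read literally, entry to the efficacy set can depend on the month 6 result (minor)

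*Combined protocol and SAP*

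**What the plan says.** Section 6.1 sets evaluability by two conditions: "Subjects who have completed 6 or more doses of Durvalumab and underwent month 6/week 26 bladder biopsy would be considered evaluable". It adds: "Subjects who completed less than 6 doses of durvalumab will not be considered evaluable". Section 11.1.2 builds the efficacy set from "Subjects who have completed at least 6 treatments of every 4 week Durvalumab IV infusions and underwent the month 6 mapping biopsy", and also plans an intention-to-treat analysis of "all subjects who have completed at least one dose of Durvalumab and underwent the month 6 mapping biopsy". No section gives a date at which the dose count closes.

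What follows the biopsy depends on its result. Under section 9, a subject whose CIS persists at month 3 is dosed "until the month 6 bladder biopsy documented persistent CIS or progression to the muscle invasive stage", and section 3.1 takes subjects with persistent CIS at month 6 off study. A subject without CIS continues towards 13 doses over 12 months (sections 3.1, 5.1.2 and 6.2).

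On gaps in dosing, section 5.1.2 says: "Subjects who have a dose interruption due to toxicity at any point in the first 12 months of treatment may resume treatment". Several Appendix A rules also hold the drug and allow it to resume after a steroid taper of at least 28 days. Sections 4.3 and 6.3, in contrast, call for permanent discontinuation when toxicity needs delays beyond two weeks or prolonged steroids.

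Sections 4.4 and 6.1 replace early withdrawals to reach 34 evaluable subjects. Section 11.2 states the boundaries (3 of 13, 9 of 34) without naming an analysis set. The interim section (11.2.3, Interim analyses) counts 13 enrolled subjects who have had the month 6 biopsy and mentions no dose minimum.

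**The concern.** Take two subjects who reach the month 6 biopsy with five doses each. The one without CIS stays on treatment and can receive a sixth dose afterwards. Both conditions are then met, and the subject enters the efficacy set as a responder. The one with persistent CIS stops at five doses and is excluded. They had the same exposure when the endpoint was measured, and only the endpoint separates them.

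This differs from the loss of subjects who never have a month 6 biopsy, because here both were biopsied. The selection removes non-responders and keeps responders, so it can only raise the apparent response rate. If the six-dose set is the one compared with the boundaries, a shift of one subject can matter.

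**Working it through.** **1. Can a subject reach the biopsy with five doses?** The schedule of assessments puts infusions at week 0 and every four weeks after that, so dose 6 is due at week 20 and dose 7 at week 24. The biopsy is at week 26 ± 14 days, that is, weeks 24 to 28.
- Missed infusions: seven are due by week 24, and 7 − 2 = 5. If the biopsy is done at week 24 before that day's infusion, only six have been due, and one miss leaves five.
- Delays of two weeks each: with k delays, dose 6 falls at week 20 + 2k. Three delays give week 26, four give week 28 and five give week 30.

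The case is reachable, but it needs real slippage.

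**2. The plan's own figures.** With n1 = 13, r1 = 3, n = 34 and r = 9,

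P(reject | p) = Σ (x = 4 to 13) P(X1 = x) · P(X2 ≥ 10 − x), where X1 ~ Bin(13, p) and X2 ~ Bin(21, p).

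At p = 0.18 this is 0.0473, and at p = 0.40 it is 0.8031. The probability of early stopping at p = 0.18 is 0.8061. All three agree with the table in section 11.2. Rejection here means 10 or more responses. Section 11.2 also mentions rejection at 9 or more, which would give 0.0819 and is a separate inconsistency.

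**3. Size of the selection effect.** Two quantities are needed, and the documents give neither:
- f, the share of biopsied subjects with fewer than six doses at the biopsy;
- s, the chance that a responder among them later reaches six doses.

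Assume that being short-dosed is unrelated to response, that no short-dosed non-responder reaches six, and that the six-dose set is used at both stages. The apparent rate is then

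p_e = p(1 − f + fs) / [p(1 − f + fs) + (1 − p)(1 − f)].

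Example with p = 0.18, f = 0.05, s = 1: 0.18 / (0.18 + 0.82 × 0.95) = 0.18 / 0.959 = 0.1877. Putting p_e through the formula in step 2 gives these rejection probabilities when the true rate is 18%:

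| f | s = 25% | s = 50% | s = 100% |
|---|---|---|---|
| 2% | 0.048 | 0.050 | 0.052 |
| 3% | 0.049 | 0.051 | 0.055 |
| 5% | 0.050 | 0.053 | 0.060 |
| 10% | 0.054 | 0.061 | 0.076 |
| 20% | 0.062 | 0.080 | 0.123 |

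In head count, f = 5% at an 18% response rate means 34 × 0.05 × 0.18 ≈ 0.3 short-dosed responders among 34 subjects.

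**4. After the change.** If only doses before the biopsy count, responders and non-responders are both kept with probability 1 − f. Then p_e = p(1 − f) / [p(1 − f) + (1 − p)(1 − f)] = p, and type I error returns to 0.0473. With no dose minimum, every biopsied subject counts and p_e = p again.

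**The case against.** The natural reading is that the six doses come first and the biopsy follows. Six doses are due by week 20, so the rule looks like a minimum exposure before the week 26 assessment, and counting later doses would serve no purpose. That is probably the intent. It does not settle the matter, because an analyst working from the final data could apply the written rule either way.

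The two-week limit in sections 4.3 and 6.3 also narrows the case. A subject discontinued under it at five doses never receives a sixth, whatever the biopsy shows, so the exclusion is symmetric. This stands where the limit is applied, but section 5.1.2 and the Appendix A hold-and-resume rules point the other way. Missed visits and repeated short delays also remain possible. Further, a non-responder who is dosed before the pathology report arrives could reach six, which reduces the asymmetry without removing it.

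Finally, the ITT set in section 11.1.2 includes both five-dose subjects and does not have this asymmetry. That is correct and limits the harm, though the plan does not tie the boundaries to that set.

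Two stronger readings are tempting. A reader might infer that the interim decision is affected because a five-dose responder's status is still open at that look. The interim section does not support this: it counts subjects with the month 6 biopsy and sets no dose condition. A reader might also infer that the six-dose set definitely drives both decisions. Sections 4.4 and 6.1 tie only the total of 34 to evaluable subjects, and section 11.2 names no set.

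**Conclusion.** The point holds as a gap in wording, of minor severity. Followed literally, sections 6.1 and 11.1.2 let membership of the efficacy set depend on the outcome, with bias towards a higher response rate. The number of subjects affected is probably small. It is small if the two-week limit in 4.3 and 6.3 is applied, and larger under 5.1.2 and Appendix A.

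On the assumptions in the working, f of 2 to 5% with s of 25 to 100% takes type I error from 0.0473 to between about 0.048 and 0.060. The values 0.076 (f = 10%) and 0.123 (f = 20%) are worst cases in which every short-dosed responder reaches six. A reader might take 0.123 as the trial's actual error rate, but nothing in the documents supports f = 20% or s = 100%. All these figures also presume that the boundaries are applied to the six-dose set, which the plan leaves open.

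**What to change.** Choose one of two options:
- In 6.1 and 11.1.2, require at least six doses received before the month 6 mapping biopsy, with the count fixed on the biopsy date and later doses ignored.
- Apply the 3/13 and 9/34 boundaries to all treated subjects who have the month 6 biopsy, without a dose minimum.

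In either case, name the set to which the boundaries apply and state that it is the same at the interim and final analyses. Separately, reconcile sections 4.3 and 6.3 with 5.1.2 and Appendix A on delay and resumption. Which rule should govern is a clinical decision outside this point.

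The cost is one clause in two sections plus a sentence in 11.2, with no change to dosing or visits. The first option loses an occasional five-dose responder from the efficacy set. The second avoids that loss but gives up the minimum-exposure condition for the decision.
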